4.7 Lost to Follow-Up

A participant will be considered lost to follow-up if he or she fails to return for scheduled study visits and is unable to be contacted by the study site staff.

The following actions must be taken if a participant fails to return to the clinic for a required study visit:

The site will attempt to contact the participant and reschedule the missed visit(s) and counsel the participant on the importance of maintaining the assigned visit schedule and ascertain if the participant wishes to and/or should continue in the study.

Before a participant is deemed lost to follow-up, the Investigator or designee will make every effort to regain contact with the participant (where possible, three (3) telephone calls and, if necessary, a certified letter to the participant's last known mailing address or local equivalent methods). These contact attempts should be documented in the participant's medical record or study file.

Should the participant continue to be unreachable, he or she will be considered to have withdrawn from the study with a primary reason of lost to follow-up.

5 STUDY VISITS AND PROCEDURES

5.1 Screening Visit (Day -21 to -1)

Subjects presenting with upper limb spasticity will be examined to verify the diagnosis of spastic hemiparesis. Then, subjects with upper limb spasticity will be screened to determine if they meet the study eligibility criteria. Prospective study participants will be informed of the study, and the requirements for study participation will be explained to them. Subject informed consent must be obtained prior to conducting screening procedures. Refer to **Table 1.1. Schedule of Study Assessments and Procedures** for activities to be performed.

At screening, protocol-specified procedures include:

- Physical and neurological examinations
- Laboratory: serum chemistry, hematology, PT/INR,
- Urinalysis
- Concomitant medications

- Medical/surgical and neurological history
- 12-lead electrocardiogram
- Columbia-Suicide Severity Rating Scale (C-SSRS) Baseline/Screening version
- Modified Ashworth Scale (MAS)
- Disability Assessment Scale (DAS)
- Tardieu Scale (TS)
- Active Range of Motion (AROM)

Results from clinical laboratory tests and centrally-read ECGs must be obtained and reviewed by the investigator. WOCBP with a positive pregnancy test must be excluded from study entry.

Before enrolling WOCBP in this clinical trial, investigators must review guidelines about study participation for WOCBP. The topics should generally include:

- Informed consent document
- Pregnancy prevention information
- Risks to unborn children
- Any drug interactions with hormonal contraceptives
- Contraceptives in current use
- Guidelines for the follow-up of a reported pregnancy

A female is considered to be of childbearing potential UNLESS she is post-menopausal (no menses for 12 consecutive months) or without a uterus and/or both ovaries.

WOCBP and male subjects must, accordingly, use an effective method of birth control such as oral contraceptive, injection, implant, patch, vaginal ring, intrauterine coil or device, tubal ligation, and female/male condom with either cap, diaphragm, or sponge with spermicide (double barrier methods). True abstinence (i.e. no heterosexual intercourse) when it is in line with preferred and usual lifestyle, or having a vasectomized partner is considered acceptable methods of contraception. Effective methods of contraception must be used from the start of study, Screening visit, to 30 days after the end of study participation.

Prior to study enrollment, WOCBP and male subjects must be advised of the importance of avoiding pregnancy during participation in this clinical study from the Baseline visit to 30 days after the end of study participation, and the potential risk factors for an unintentional pregnancy. The subject must sign the informed consent document stating that the above-mentioned risks/consequences were discussed with her/him.

During the study, all WOCBP should be instructed to contact the investigator immediately if they suspect they might be pregnant (e.g., missed or late menstrual cycle). The investigator must immediately notify the sponsor or the authorized representative of any female subject who becomes pregnant any time during study participation. The site will be asked to follow-up with the subject periodically during the pregnancy for ongoing health and safety information through term, as applicable. Given that this is a single treatment administration study, subjects who become pregnant after receiving their study treatment will not be automatically discontinued from the study.

After the required screening procedures are completed and study eligibility is confirmed, the subject is enrolled in the study and randomized to a treatment arm.

DaxibotulinumtoxinA for Injection for Adult Upper Limb Spasticity Protocol 1820203 Amendment 2	Version 6 xx June 2020
5.3 Follow-up Visits	
The following procedures will be completed at follow-up visits:	
• Vital signs (blood pressure [BP], pulse, temperature) and weight	
Columbia- Suicide Severity Rating Scale (C-SSRS)- Since Last Visit version	

5.4 End of Study Visit

A participant is considered to have completed the study when the MAS score has returned to baseline levels and the PGIC ≤ 0 , or the Week 36 visit whichever comes first and has completed the last scheduled procedure shown in Table 1.1. Schedule of Study Assessments and Procedures.

Subjects enrolled post COVID-19, after 20 March 2020 will have the EOS Visit at Week 12 as shown in Table 1.2. Table 1.1. Schedule of Study Assessments **and Procedures**.

The EOS Visit may also occur when a subject prematurely withdraws from the study for specific reasons (e.g., AEs, pregnancy, or withdraws consent).

6 SAFETY ASSESSMENTS

6.1 Clinical Laboratory Tests

A central laboratory will be used to process all clinical specimens. The clinical laboratory parameters that will be evaluated in the study are listed in Table 3.

Hematology	Chemistry	Urinalysis	Additional Tests
Hemoglobin	Sodium	Specific gravity	
Hematocrit	Potassium	pH	
Leukocyte count	Chloride	Glucose	
(total)	CO ₂	Protein	
Leukocyte count (differential)	Calcium	Blood	
Red blood cell count	Albumin	Bilirubin	PT/INR
Platelet count	Glucose	Ketones	
	Total bilirubin		
	Alanine aminotransferase		

Table 4.Clinical Laboratory Parameters

DaxibotulinumtoxinA for Injection for Adult Upper Limb Spasticity Protocol 1820203 Amendment 2		Version 6 xx June 2020	
	Aspartate aminotransferase Alkaline phosphatase		
	Blood urea nitrogen Creatinine		

CO₂=carbon dioxide; ET=early termination; WOCBP=women of childbearing potential.

It is the Investigator's responsibility to review the results of all laboratory tests as they become available. For each laboratory test result outside the reference range, the Investigator must ascertain if the abnormal lab result is a clinically significant result for that individual subject. Likewise, if laboratory tests are taken at follow-up visits, the Investigator must ascertain if this is an abnormal and clinically significant change from pre-treatment for that individual subject. The Investigator may repeat the laboratory test or request additional tests to verify the results of the original laboratory test. The Investigator must sign and date all written laboratory results (e.g., urinalysis, hematology, chemistry, and pregnancy tests) and note Not Clinically Significant (NCS) or Clinically Significant (CS) for each out of range laboratory value.

If a laboratory value is determined to be a clinically significant result for that subject, this may be considered an AE to be assessed according to severity. Refer to Section 6.2 for further information.

6.2 Adverse Events

6.2.1 Assessment of Adverse Events:

Adverse Events (AEs) will be graded as mild, moderate, or severe as defined in Section 6.2.2.3 of this protocol.

AEs will be evaluated at the Injection visit post-treatment, follow-up Weeks 2, 4, 6, 8, 12, 16, 20, 24, 28, 32 and 36/EOS, if applicable.

Adverse events will be reported by the Sponsor in accordance with "21CRF part 312.32 and Guidance for Industry and Investigators: Safety Reporting Requirements." The Investigator will report any serious adverse events (SAEs) to the IRB.

Subjects should be told to seek immediate medical attention if they experience any abnormal symptoms after investigational product administration, especially:

- Generalized loss of strength and muscle weakness
- Difficulty swallowing, breathing or speaking
- Extreme tiredness
- Loss of bladder control
- Symptoms of allergic reaction (rash, itching, etc.)

6.2.2 Adverse Events and Serious Adverse Events

6.2.2.1 Definition of Adverse Events

For this protocol, an adverse event (AE) is any untoward medical occurrence (e.g., sign, symptom, disease, syndrome, intercurrent illness, clinically significant abnormal laboratory finding, injury or accident) that emerges or worsens following administration of investigational product and until the end of trial participation that may not necessarily have a causal relationship to the administration of the investigational product. An AE can therefore be any unfavorable and/or unintended sign (including a clinically significant abnormal laboratory result), symptom, or disease temporally associated with the use of an investigational product, whether or not considered related to the investigational product. A treatment-emergent AE (TEAE) is one that occurs after any period of exposure to treatment.

Pre-existing conditions, which increase in frequency or severity or a change in nature as a consequence of an investigational product use will also be considered an adverse event.

An unexpected AE is an adverse reaction, the nature or severity of which is not consistent with the applicable product information (e.g., Investigator's Brochure for an unapproved investigational product or package insert/summary of product characteristics for an approved product). Any clinically significant change in the study safety evaluations, (e.g., vital signs, laboratory results, ECG, injection site evaluation, physical/neurological examinations, etc.) post-treatment must be reported as an AE.

6.2.2.2 Definition of Serious Adverse Events (SAE)

A serious adverse event (SAE) is any untoward medical occurrence that results in any of the following outcomes:

- Death
- Life-threatening, (i.e., the subject was, in the opinion of the Investigator, at immediate risk of death from the event as it occurred. It does not apply to an AE that hypothetically might have caused death if it were more severe)
- Persistent or significant disability/incapacity or substantial disruption of the subject's ability to carry out normal life functions
- Requires in-patient hospitalization or prolongs hospitalization (i.e., a prolonged hospitalization beyond the expected length of stay; hospitalizations for elective medical/surgical procedures, scheduled treatments, or routine check-ups are not SAEs by this criterion)
- Congenital anomaly/birth defect (i.e., an adverse outcome in a child or fetus of a subject exposed to the molecule or investigational product before conception or during pregnancy)
- Does not meet any of the above serious criteria but based upon appropriate medical judgement may jeopardize the subject or may require medical or surgical intervention to prevent one (1) of the outcomes listed above (i.e., is a significant or important medical event)

DaxibotulinumtoxinA for Injection for Adult Upper Limb Spasticity	Version 6
Protocol 1820203 Amendment 2	xx June 2020

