6.2.2.4 Time Period and Frequency for Event Assessment and Follow-Up

The occurrence of an adverse event (AE) or serious adverse event (SAE) may come to the attention of study personnel during study visits and interviews of a study participant presenting for medical care, or upon review by a study monitor.

All AEs including local and systemic reactions not meeting the criteria for SAEs will be captured on the appropriate case report form (CRF). Information to be collected includes event description, time of onset, clinician's assessment of severity, relationship to study product (assessed only by those with the training and authority to make a diagnosis), and time of

resolution/stabilization of the event. All AEs occurring while on study must be documented appropriately regardless of relationship. The investigator will assess subject post-treatment and at each subsequent study visit for the occurrence of AEs. All AEs will be followed to adequate resolution.

Any medical condition that is present at the time that the participant is screened will be considered as baseline and not reported as an AE. However, if the study participant's condition deteriorates at any time during the study, it will be recorded as an AE.

Changes in the severity of an AE will be documented to allow an assessment of the duration of the event at each level of severity to be performed. AEs characterized as intermittent require documentation of onset and duration of each episode.

The investigator should follow the SAE until it resolves or is determined by the investigator to be stable, or the subject is lost to follow-up. The investigator should continue to report any significant follow-up information to the sponsor or the authorized representative, and the IRB, up to the point the event has resolved, or is determined to be stable. Resolution means the subject has returned to the baseline state of health, and stable means the investigator does not expect any further improvement or worsening of the subject's condition.

Any new SAEs reported by the subject to the investigator that occur after the last scheduled contact and are determined by the investigator to be reasonably associated with the administration of investigational product should be reported to the sponsor or the authorized representative, and the IRB, as required.

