6.2.2.6 Serious Adverse Event Reporting

An Investigator must report an SAE to Revance or the designated CRO representative within **24 hours** of their awareness of the event:

- 1. Complete and return an SAE Form with all information known to date; including the Investigator's assessment of causality.
- 2. A fatal or life-threatening SAE must be telephoned to Revance or the authorized representative as soon as the Investigator learns of the event.
- 3. All pertinent medical records (discharge summary, autopsy report, etc.) should be obtained and judgments of all medical personnel who assisted in subject's treatment and follow-up.
- 4. Provide follow-up information to Revance or the authorized representative.

All SAEs will be followed until satisfactory resolution or until the Investigator deems the event to be chronic or the participant is stable. Other supporting documentation of the event may be requested by the Data Coordinating Center (DCC)/study sponsor and should be provided as soon

as possible. The study sponsor will be responsible for notifying the FDA of any unexpected fatal or life-threatening suspected adverse reaction as soon as possible, but in no case later than 7 calendar days after the sponsor's initial receipt of the information. In addition, the sponsor must notify FDA and all participating investigators in an Investigational New Drug (IND) safety report of potential serious risks, from clinical trials or any other source, as soon as possible, but in no case later than 15 calendar days after the sponsor determines that the information qualifies for reporting. Regulatory authorities, IRBs, and Investigators will be notified of SAEs in accordance with applicable regulations and requirements (e.g., GCPs, ICH Guidelines, national regulations and local requirements).

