9.3. Adverse Events

AEs will be coded using MedDRA version 22 or later. An AE will be considered treatment emergent if the event begins on or after the study medication dose date or if the event begins before and worsens in severity after the study medication dose date. An adverse event with a relationship to study medication of definite, probable, or possible is also considered to be treatment-emergent.

AEs will be summarized by system organ class (SOC) and preferred term (PT). An AE is considered related to study treatment if the relationship is considered as definite, probable, or possible. If the relationship to study treatment is missing, the AE will be counted as definite in summary tables. If the severity is missing, then the AE will be counted as severe in summary tables. Actual missing values will be presented in the listings.

Summary tables will be provided for treatment-emergent AEs (TEAEs) for the following:

- Overall summary of TEAEs
- TEAEs by SOC and PT
- TEAEs by SOC and PT occurring in at least 5% of subjects
- TEAEs by SOC, PT, and maximum severity
- TEAEs by SOC, PT, and strongest study medication relationship
- Treatment-related TEAEs by SOC and PT
- Serious TEAEs by SOC and PT
- TEAEs resulting in study medication discontinuation by SOC and PT

[REDACTED]

The overall summary of TEAEs will include the number and percentage of subjects with a TEAE, with treatment-related TEAEs, with serious TEAEs, [REDACTED], and with TEAEs leading to death. For TEAE summaries, the number and percentage of subjects will be presented by SOC and PT by treatment. Subjects will be counted only once for each SOC and for each PT within each SOC. For summaries by maximum severity and strongest relationship, if a subject has the same event more than once, the subject will be included only once at the worst severity or strongest relationship. Summary tables by SOC and PT will be sorted in descending frequency by SOC and then by PT within each SOC by the DAXI 500 U column. All AEs will be included in the listings. Listings will be provided for all AEs, serious AEs, and AEs resulting in study medication discontinuation.

This document is confidential.

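### The elective/scheduled-admission exemption in the SAE definition is not tied to planning before injection or to an unworsened prior condition, so a post-injection event treated by a booked admission can go unflagged as serious

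*Protocol*

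**What the plan says.** Protocol 6.2.2.2 lists the outcomes that make an untoward occurrence serious. The hospitalization bullet reads "Requires in-patient hospitalization or prolongs hospitalization (i.e., a prolonged hospitalization beyond the expected length of stay" and, inside the same parenthesis, exempts a class of admissions: "hospitalizations for elective medical/surgical procedures, scheduled treatments, or routine check-ups are not SAEs by this criterion". The last bullet is the important-medical-event route. It applies to an event that "Does not meet any of the above serious criteria but based upon appropriate medical judgement may jeopardize the subject", or that may need intervention to prevent one of the listed outcomes.

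Two neighbouring sections deal with timing. Section 6.2.2.1 defines an AE as an occurrence "that emerges or worsens following administration of investigational product and until the end of trial participation". Section 6.2.2.4 says "Any medical condition that is present at the time that the participant is screened will be considered as baseline and not reported as an AE", and then that deterioration during the study is recorded as an AE.

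Two provisions depend directly on SAE status. Section 6.2.2.6 begins "An Investigator must report an SAE to Revance or the designated CRO representative within" and sets the limit at 24 hours from awareness. SAP 9.3 lists a table of "Serious TEAEs by SOC and PT".

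**The concern.** The exemption depends on how an admission was arranged (elective, scheduled, routine), not on when its cause arose. Such a clause is useful for keeping out admissions that have nothing to do with the trial, such as a procedure booked before injection for an old, unchanged problem. As worded, it also takes in an in-patient admission arranged during follow-up to treat something new or worse.

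What is at stake is how the event is classified and which actions follow. An event left out of the hospitalization criterion, and not picked up by another one, does not trigger the 24-hour report and does not appear in the serious TEAE table. Section 7.2 also does not require non-serious unanticipated events to be reported to the IRB or the sponsor, and the provisions in 6.2.2.4 and 6.2.2.7 for new events after the last scheduled contact cover only SAEs.

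**Working it through.** The plan states no figure on this point and no arithmetic applies. The check is whether any text limits the exemption, and what the wording does to specific cases.

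**Step 1: look for a limit elsewhere.**

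- Protocol 6.2.2.1 fixes the AE window at injection onwards. It decides what is an AE and says nothing about which admissions are exempt.
- Protocol 6.2.2.4 treats conditions present at screening as baseline. It too decides only whether something is an AE.
- Protocol 6.2.2.5 to 6.2.2.7, 7.1, 7.2 and 10.5 use SAE status for reporting, follow-up or review and do not redefine it.
- SAP 9.3 defines treatment-emergent by onset or worsening relative to the dose date. Its visible text does not define seriousness.

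No visible text limits the exemption.

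**Step 2: apply the wording to cases.**

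| Case | Hospitalization criterion, literal reading | With the limit proposed under the fix |
|---|---|---|
| Old, unchanged condition; procedure planned before injection | Exempt | Exempt |
| New event after injection; unplanned admission | Serious | Serious |
| New event after injection; admission booked later to treat it | Exempt | Assessed under the criterion |
| Old condition that worsens after injection; booked admission | Exempt | Assessed under the criterion |

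Only the third and fourth rows differ. Both are AEs under 6.2.2.1 and treatment-emergent under SAP 9.3, so they belong to the set that the serious TEAE table draws on.

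**Step 3: follow those two rows through the plan.**

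- *Still available:* every other criterion in 6.2.2.2, because the exemption is confined to the one bullet. Unless the event was also life-threatening, disabling or fatal, the usual route is the important-medical-event bullet, which is a matter of medical judgement. With up to 35 centers, identical cases can be called differently.
- *Kept in any case:* CRF capture as an AE (6.2.2.4), DMC review, which covers AEs as well as SAEs (10.5), and the general TEAE tables by SOC and PT, severity and relationship (SAP 9.3).
- *Lost if no other criterion is applied:* the serious flag, the 24-hour report and the serious TEAE entry.
- *Hard to recover later:* the items that 6.2.2.4 lists for collection on each AE do not include hospitalization, and no visible SAP table counts hospitalized AEs that were not flagged serious.

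**The case against.** The strongest reply is that the three exempt categories read naturally as admissions not driven by an event, so that an admission needed to treat a new AE is one that the AE requires and is serious. Many investigators would read it that way. But the text does not say so, and *scheduled treatments* is broad enough to cover the other reading. This reply turns a certain misclassification into a possible one; it does not remove the inconsistency between sites.

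A second reply is that the important-medical-event bullet is a real safety net, since it reaches events that may need surgical or medical intervention. That stands, and it narrows the gap. Nor can one answer that hospitalization was meant to be the objective criterion: the protocol does not say this, and it uses investigator opinion for the life-threatening criterion as well.

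Third, many cases that come to mind would be serious anyway. A new vascular event followed by a booked procedure would often already qualify through acute admission, threat to life or disability, and the later admission would then be follow-up of an existing SAE. That also stands.

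Two stronger readings should be set aside. A reader might infer that these events vanish from safety review; they do not, for the reasons in step 3. A reader might also infer that SAE incidence is biased between arms. The trial is double-blind, the rule is the same in every arm, and the documents offer no mechanism for differential loss.

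**Conclusion.** The point holds as a defect of wording in a safety definition. The exemption has no condition on when the admission was planned or on whether the condition pre-existed unworsened. Read literally, it takes a booked in-patient admission for a post-injection AE out of the hospitalization criterion. The direction is clear: literal use can only lower the number of SAEs, never raise it.

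The size cannot be given, because the documents state no rate of SAEs or of elective or scheduled admissions. A reader might divide 128 subjects by four arms, assuming equal allocation, and note that one subject is 1/32 = 3.1 percentage points of an arm. That describes any single misclassified subject and says nothing about whether one is to be expected. Nor does follow-up of up to 36 weeks apply to everyone: subjects enrolled after the hold of 20 March 2020 finish at Week 12, and others may end from Week 12 once effect is lost.

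The conclusion assumes that no limiting text lies in redacted parts. The bullet list in 6.2.2.2 reads as complete, but some adverse-event text in the SAP is redacted. This is a small, worthwhile clarification, with no demonstrated effect on any efficacy analysis or on the comparison between arms.

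**What to change.** Replace the exemption in Protocol 6.2.2.2 with wording to this effect:

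> *In-patient admissions planned before injection, or routine check-ups, for a condition that existed before injection and has not worsened since, are not SAEs by this criterion; an in-patient admission for an event that emerged or worsened after injection is assessed under this criterion even if scheduled.*

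The anchor should be injection, as in 6.2.2.1, and not screening, as in 6.2.2.4. Screening may precede injection by up to 21 days. With a screening anchor, a condition that arose in that interval and had a procedure booked before injection would fall outside the exemption, although it is not an AE under 6.2.2.1.

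Before database lock, query admissions recorded as elective or scheduled against the new wording. If the CRF has no field for hospitalization, the query will have to work from event descriptions and source records.

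The cost is one sentence, a short query round that may reclassify events already collected under the existing definition, a slightly higher SAE count and a few more 24-hour reports.
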